**List of abbreviations and relevant definitions**

AE	Adverse Event
ASE/EAE	American Society of Echography / European Association of Echography
BC	Breast Cancer
BLOOD	Circulating biomarkers
CAC	Calcium artery calcium
3D CRT	Three Dimensional Conformal Radiation Therapy
CT	Cardiac Computed tomography
CTCA	Computed tomography coronary angiography
CRF	Case Report Form
CTCAE	Common Terminology Criteria for Adverse Events
CTV	Clinical Target Volume
DCIS	Ductal Carcinoma In Situ
DICOM	Digital imaging and communications in medicine,
DVH	Dose Volume Histogram
ECHO-ST-ST	2D-speckle-tracking echocardiography
ENACT	Enabling Communication Technology
GLS/GLSR	Global and Segmental Longitudinal Strain and Strain Rate
Gy	Gray
IC	Informed Consent
IHD	ischemic heart disease
IMRT	Intensity modulated radiotherapy
MREC	Medical research ethics committee (MREC)
LVEF	Left Ventricular Ejection Fraction
MAPSE	Mitral annular plane systolic excursion
MRI	Cardiac magnetic resonance imaging
NTCP	Normal Tissue Complication Probability
OAR	Organ At Risk
PTV	Planning target volume
RT	Radiotherapy
Sponsor	The sponsor is the party that commissions the organisation or performance of the research, for example a pharmaceutical company, academic hospital, scientific organisation or investigator. A party that provides funding for a study but does not commission it is not regarded as the sponsor, but referred to as a subsidising party.
Sv	Sievert
TAPSE	Tricuspid annular plane systolic excursion
VMAT	volumetric modulated arc therapy
WMO	Medical Research Involving Human Subjects Act (in Dutch: Wet Medisch-wetenschappelijk Onderzoek met Mensen)

## 1. TWO-PAGE OUTLINE OF THE PROTOCOL

**1.1. Background:** Breast cancer (BC) radiotherapy (RT) leads to coincidental radiation of the heart, resulting in increased risk of a variety of heart diseases. The prevalence of BC survivors at risk of cardiac complications will gradually increase, as the incidence of BC in Europe is still rising while prognosis significantly improved over the last decades. These late cardiac complications have a major impact on quality of life and lead to subsequent morbidity and increased mortality. Therefore, identifying BC patients with the highest-risk of radiation-induced cardiac complications is crucial for developing strategies for primary and secondary prevention, which may contribute to healthy ageing. So far, little has been done on the relationship between dose distribution to different anatomical cardiac structures during RT and early cardiovascular changes that may lead to cardiac complications.

**1.2. Main study objective:** The main objective is to identify and validate the most important cardiac imaging (ECHO-ST, CTCA and MRI) and circulating biomarkers of radiation-induced cardiovascular changes arising in the first 2 years after breast cancer radiotherapy.

**1.3. Study design:** An international multicenter prospective cohort study

**1.4. Endpoints:** The primary endpoint is defined as a mean decrease in Global and Segmental Longitudinal Strain and Strain Rate (GLS/GLSR) of at least 2.5% assessed by cardiac ultrasound 6 to 24 months after RT compared to baseline.

The secondary endpoints are:

- Changes in myocardial function assessed by cardiac ultrasound 6 to 24 months after RT compared to baseline.
- Anatomical changes in coronary artery atherosclerosis (number of coronary segments containing any plaque/stenosis, and calcium score) by cardiac CT 24 months after RT compared with baseline. The endpoint is defined as 15% or greater changes.
- Myocardial changes by MRI 6 to 24 months after RT compared with baseline (morphology, function, tissue characterization by delayed enhancement and pre-/post-contrast T1 mapping). The endpoint is defined as an increase of the mean T1 mapping value of at least 7%.
- Temporal changes in circulating biomarkers at the end of RT and 6 to 24 months after RT compared with baseline. The endpoint is defined as a significant increase or decrease in each biomarker between time points.

**1.5. Selection criteria:** Female unilateral BC patients aged 40-75 years treated with primary breast conserving surgery and postoperative radiotherapy using modern planning-CT based RT technologies.

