### 3. OBJECTIVES OF THE TRIAL

#### 3.1. General objectives

MEDIRAD-EARLY HEART is part of the MEDIRAD project. The MEDIRAD project aims to enhance the scientific basis and clinical practice of radiation protection in the medical field and thereby addresses the need to understand and evaluate the health effects of low dose ionizing radiation exposure from diagnostic and therapeutic imaging and from off-target effects in radiotherapy.

MEDIRAD will pursue 3 major operational objectives: First, it will improve organ dose estimation and registration to inform clinical practice, optimize doses, set recommendations and provide adequate dosimetry for clinical-epidemiological studies of effects of medical radiation. Second, it aims to evaluate and understand the effects of medical exposures, focusing on the two major endpoints of public health relevance: cardiovascular effects of low to moderate doses of radiation from RT in BC treatment including understanding of mechanisms; and long-term effects on cancer risk of low doses from CT in children. Third, it will develop science-based consensus policy recommendations for the effective protection of patients, workers and the public.

The specific objective of the MEDIRAD-EARLY HEART study is to gain more insight in the relationship between radiation dose distributions to the heart, to different anatomical cardiac substructures, during RT and early cardiovascular changes (within two years).

**Primary objective:** to identify the most important cardiac imaging (ECHO-ST, CT and MRI) and circulating biomarkers of radiation-induced cardiovascular changes arising in the first 2 years after BC RT and to develop Normal Tissue Complication Probability (NTCP) models integrating these biomarkers combined with dose metrics of cardiac structures based on 3D-dosimetry.

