**Secondary objectives:**

- To formulate recommendations for implementation of these multivariable NTCP models in primary and secondary prevention strategies to ultimately develop stratified therapeutic and diagnostic approaches (overarching aim of MEDIRAD):
  - Improvement of RT planning techniques to spare cardiac structures, or even selection for proton therapy;
  - First guidelines for cardiac follow up programs in high-risk BC patients;
- To implement a European repository of patient dose and imaging data (overarching aim of MEDIRAD WP2.4.1).

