### 9.2. Sample Size

The sample size was based on a statistical power of 80%, an alpha-risk of 5%, the definition of the primary endpoint (a decrease in the global and segmental longitudinal strain or strain rate of at least 2.5%) and baseline measurements hypothesis (mean global longitudinal strain before RT : -16.5%  $\pm$  2.1% from Dalen et al, European Journal of Echocardiography : the Journal of the Working Group on Echocardiography of the European Society of Cardiology. 2010) Considering paired test for comparisons, but also possible lost to follow-up due to death or other reason, the inclusion of 250 women is necessary for EARLY-HEART study.

Centre	Recruitment rate per month	Total number of patients to recruit in 1 year
IRSN	4.2	50
UMCG	5	70
TUM-MED	4.6	55
CCUL	2.1	25
ICO	4.2	50
Total		250

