#### *Stage II: Radiation-induced Cardiovascular Changes Models (RCCM)*

The Radiation-induced Cardiovascular Changes Models (RCCM) aim to investigate the dose-

response relationships between 3D-dimensional dose distributions in cardiac substructures and cardiovascular changes in term of imaging and circulating biomarkers time-kinetics occurring in the 2 years after radiotherapy for breast cancer (before RT, 6 and 24 months after RT).

To investigate the time course of continuous variables extracted from ECHO-ST, CT or MRI measurements, mixed regression models are used since these longitudinal data present a hierarchical structure where serial measurements are nested within individuals over time. In this framework, a variable selection is possible by an AIC or BIC model selection or by incorporating a lasso or an elastic net penalty especially for the imaging and circulating biomarkers selection. To investigate some non-linear predictor effects, a fractional polynomial approach could be considered.

The radiation exposure could be included in this model by several ways: point wise dosimetric parameters (mean dose,  $D_x$  or  $V_x$ ), DVH reduction equivalent uniform dose (EUD) or through a functional data analysis approach by estimating a functional coefficient associated to a functional predictor (here the DVHs or the probability density function).

To exploit the richness of the longitudinal global or regional strain curves, a myocardial deformation analysis will be conducted using a functional mixed effect model to deal with the infinite-dimensional functional responses measured at multiple time points.

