### *Stage III: NTCP and functional NTCP models (F-NTCP).*

In presence of cardiac toxicity outcome, a multimetric NTCP modelling is constructed through time-dependent covariates and time dependent coefficients Cox model.

The individualized risk estimation is calculated from an integrative clinical-biologic risk score obtained at the end of a variable selection process (lasso or elastic-net partial likelihood penalization for example).

The radiation exposure could be included in this model by several ways: point wise dosimetric parameters (mean dose,  $D_x$  or  $V_x$ ), DVH reduction equivalent uniform dose (EUD).

Using a time-dependent Cox regression performed in a functional data analysis way, a functional NTCP model (F-NTCP) will provide a volume-effect functional parameter which allows a risk weighting across the considered dose range and especially for the lowest one.

Furthermore, as a complementary approach for cardiovascular risk modelling, the cardiac imaging and circulating biomarkers will be integrated into a mechanistic model of cardiovascular disease, including atherosclerosis (Work package 4.3 Cardiovascular risk modelling, HMGU).

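### The plan aims to validate biomarkers and build an individual risk score but specifies no internal validation or performance measure, so the score can look predictive when it is noise

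*Combined protocol and SAP*

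**What the plan says.** - **Aim.** Section 1.2 gives the main objective as to "identify and validate the most important cardiac imaging" and circulating biomarkers of radiation-induced change. The primary objective in section 3.1 is to identify them and "to develop Normal Tissue Complication Probability (NTCP) models integrating these biomarkers combined with dose metrics of cardiac structures"; validation is not mentioned there.
- **Use.** Section 1.7 intends the risk score for prediction in the individual patient. The secondary objectives in 3.1 look ahead to recommendations drawn from the NTCP models, including "First guidelines for cardiac follow up programs in high-risk BC patients".
- **Selection.** Stage II of section 9.3 says "a variable selection is possible by an AIC or BIC model selection or by incorporating a lasso or an elastic net penalty". Stage III takes its individual risk from "an integrative clinical-biologic risk score obtained at the end of a variable selection process", with penalised partial likelihood offered only as an example. Neither stage says how a penalty would be tuned.
- **Sample.** Section 9.2 concludes that "the inclusion of 250 women is necessary for EARLY-HEART study". One cohort is described, without a development/validation split or a second cohort.
- **What is absent.** Section 9.3 contains no hold-out, cross-validation, bootstrap, optimism correction, discrimination measure or calibration measure. The random checks in section 12.5 concern data quality. The mechanistic model at the end of Stage III is described as complementary risk modelling, not as validation of the score.

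**The concern.** The candidate set is large for the sample. Section 3.2.2 names 46 blood markers plus DNA methylation, and section 7.5 samples blood at four times. Section 3.2.2 also lists fifteen secondary echocardiographic measures, besides CT and MRI parameters. Stage II adds mean dose, Dx, Vx, EUD and functional dose-volume predictors.

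A model chosen from so many candidates fits the women who chose it better than it will fit anyone else. Without an estimate that allows for the selection, a reader cannot tell how much of the apparent performance is real. Followed as written, the plan cannot deliver the validation named in 1.2, and it gives no basis for judging whether the score is fit for the individual prediction named in 1.7. A development-only aim, as in 3.1, would still need an honest performance estimate for that use.

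**Working it through.** **1. The plan's own figure.** The documents give no figure for model performance. Their only sample size is for the paired strain comparison:

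n = (1.96 + 0.84)² × 2 × SD² × (1 − ρ) / δ²

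From 9.2: SD 2.1, and δ = 2.5% of 16.5 = 0.4125 if the decrease is read as relative. The correlation ρ is not given, and two-sided testing is assumed. With ρ = 0.5, n = 7.85 × 4.41 / 0.170 ≈ 204. Then 204/250 = 0.816, so 250 is reached with about 18% loss to follow-up. The figure is reachable under assumed values and is not disputed here. It was not derived for selecting or validating a prediction model.

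**2. Candidates.** From 3.2.2: 7 classical markers + 4 cytokines + 9 endothelial + 5 microparticles + 21 microRNAs = 46. If all were noise, independent, and each tested at 5%, the expected number of false positives per contrast would be 46 × 0.05 = 2.3. The chance of at least one is 1 − 0.95^46 = 0.91.

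**3. Apparent performance when nothing is real.** Inputs:
- From the plan: 250 women, 46 markers.
- Assumed: independent normal markers read once, outcome unrelated to all of them (true C 0.50), and 13, 25 or 50 events. Stage III gives neither an outcome definition nor an event count.
- Methods: forward selection with penalty 2 per variable (AIC) or log(events) per variable (BIC), and lasso tuned by 10-fold cross-validation. All use Cox partial likelihood, with 60, 60 and 40 runs.

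| Mean apparent C | 13 events | 25 events | 50 events |
|---|---|---|---|
| Forward AIC | 0.86 | 0.79 | 0.70 |
| Forward BIC | 0.82 | 0.73 | 0.63 |
| Lasso, all runs | 0.59 | 0.57 | 0.57 |
| Lasso, empty model | 72% | 68% | 58% |
| Lasso, when not empty | 0.82 | 0.73 | 0.67 |

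The lasso rows agree with each other. At 13 events, 0.28 × 0.82 + 0.72 × 0.50 = 0.59. With 60 runs the standard error of the 28% non-empty share is √(0.28 × 0.72/60) = 6 percentage points, so the percentages are approximate.

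A logistic version (200 runs per setting) gave a new-data AUC of 0.50 throughout, against an apparent AUC of 0.90, 0.81 and 0.73 with AIC. Raising the candidates to 63 at 25 events raised the apparent AUC to 0.86.

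**4. Which correction works.** Logistic version, forward AIC, noise only:

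| AUC | 25 events | 50 events |
|---|---|---|
| Apparent | 0.82 | 0.73 |
| Bootstrap optimism-corrected | 0.62 | 0.56 |
| 10-fold cross-validation of the whole procedure | 0.51 | 0.50 |

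The bootstrap removes (0.82 − 0.62)/(0.82 − 0.50) = 63% of the excess at 25 events and (0.73 − 0.56)/(0.73 − 0.50) = 74% at 50. Cross-validating the whole procedure removes nearly all of it.

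**The case against.** Several points on the other side stand.

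- **Method.** A reader might infer that the score *will* look predictive even if it is noise. The documents do not support that. AIC and BIC are named in Stage II only, beside lasso and elastic net, and the only examples given for the Stage III score are penalised methods. A tuned lasso usually returned no model at all from noise. Forward search is an assumption of the simulation. *Can* is the right word: AIC is permitted, no method is fixed for the score, no tuning rule is given, and a lasso that does select still shows an apparent C well above 0.50.
- **Reporting.** A reader might infer that inflated discrimination and calibration will be reported. The plan schedules no such measures. The defect is that performance assessment is missing, and the use of the same women throughout is inferred from there being one cohort and no split.
- **The word *validate*.** It appears in the outline and applies to biomarkers, not expressly to the risk score; 3.1 omits it. This weakens an argument that rests on the word alone. It does not answer the individual prediction intended in 1.7.
- **Clinical use.** Guidelines and treatment selection in 3.1 are eventual aims of the wider project, so it goes too far to say that they will follow directly from this score.
- **Realism.** The simulation uses fixed, independent markers, whereas Stage II is longitudinal and Stage III uses time-dependent covariates. It shows the mechanism and its plausible size; it does not forecast this study's result.

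**Conclusion.** The concern holds in a limited form. Sections 1.2 and 3.1 disagree on validation, and section 9.3 provides no means of estimating how the Stage II and III models perform beyond the data that select and fit them. A score can therefore look predictive when it is noise, and nothing in the plan would reveal it.

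The size depends strongly on a choice the plan leaves open. Against a true 0.50, mean apparent C ran from 0.57–0.59 with tuned lasso to 0.70–0.86 with forward AIC. These figures rest on the assumed event counts, independent markers and a candidate set limited to the 46 blood markers. Imaging, dose and repeated measurements would add candidates.

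The primary strain endpoint and its sample size are unaffected. The change should be made before the modelling begins, but it does not call the cohort design into question.

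**What to change.** Add to Stages II and III:

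1. The whole pipeline (selection, tuning, fitting) is repeated inside nested or repeated cross-validation, and this is the primary performance estimate. Bootstrap correction may be shown beside it but should not replace it, given the residual optimism seen under noise. Cross-validation used only to tune a penalty does not count as validation of the selected score.
2. Report corrected discrimination, calibration slope where events allow, and the selection frequency of each biomarker. State the Stage III outcome and expected number of events, so that it is clear beforehand whether calibration can be estimated.
3. Leave out each of the five centres in turn as a supportive check only. The smallest centre plans 25 women; at the assumed 25 events in 250 it would contribute about 25 × 25/250 = 2.5 events.
4. In addition, and not as a substitute, align 1.2 with 3.1 so that both state the aim as to identify and *internally validate*. Deleting the word from 1.2 would remove the contradiction but leave the score without an honest performance estimate.

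The cost is computing time and some SAP text, with no new data or visits. Reported performance will be lower than the apparent values, and a score built from weak signals may turn out to have none.

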### 1.6. Interventions:

- Cardiac imaging:
  - o Electrocardiogram to detect any arrhythmia followed by Automated 2D-speckle-tracking echocardiography (ECHO-ST), the most commonly used modality to evaluate myocardial dysfunction and a new technique of assessing myocardial deformation
  - o Computed tomography (CT) to evaluate coronary artery lesions by assessing plaques (calcified and non-calcified) and stenosis of the coronary arteries, and determination of coronary artery calcium score
  - o Cardiac magnetic resonance imaging (MRI) for the evaluation of the myocardium (including tissue abnormalities, cardiac morphology and function).
- Circulating biomarkers (BLOOD) will be based on a panel of circulating classical and novel blood-based biomarkers.

Imaging and circulating biomarkers will be assessed at baseline before RT (ECHO-ST, CT, MRI, BLOOD); at the end of RT (BLOOD); 6 months after RT (ECHO-ST, MRI, BLOOD) and 24 months after RT (ECHO-ST, CT, MRI, BLOOD).

### 1.7. Statistical considerations:

With 250 women, the study will have 80% power, with an  $\alpha=0.05$  to find a mean decrease in GLS/GLSR of at least 2.5%.

The analysis plan is divided into three parts. In the first part a descriptive analysis of the data is done. Differences in biomarkers between unexposed and paired exposed groups (e.g. right vs. left-sided breast RT) at different time points are analysed to generate preliminary hypotheses on effects of RT on the heart. To investigate the time course of continuous variables extracted from ECHO-ST, CT or MRI measurements, mixed regression models are used. In the second part (anatomical) changes in cardiac biomarkers are correlated with dose distribution data. In the third part of the analysis multivariable Normal Tissue Complication Probability (NTCP) models are constructed. An integrative clinical-biological risk score is developed for individual risk prediction.

## 2. BACKGROUND AND INTRODUCTION

### 2.1. Introduction

Radiotherapy (RT) plays an important role in the treatment of breast cancer (BC), as over 60% of all BC patients are irradiated as part of their curative treatment. BC radiotherapy generally leads to coincidental irradiation of the heart, resulting in an increased risk of a variety of heart diseases, including ischemic heart disease (IHD), congestive heart failure, arrhythmias, conduction defects, valvular disease and pericarditis with relative risks within the range of 1.2 to 3.5 by comparing left-sided BC patients (with higher exposure to the heart) to right-sided BC patients. Moreover, cardiac damage was shown to be correlated with the mean heart dose with 7.4% rate increase of acute coronary events per one Gray (95% confidence interval, 2.9-14.5;  $P < 0.001$ ), with no minimum threshold for risk, recently the risk of acute coronary events within the first 9 years after RT was confirmed by another publication.

The incidence of BC in Europe is still rising while prognosis significantly improved over the last decades. Therefore, the prevalence of BC survivors at risk for cardiac complications will gradually increase. There is a clear evidence that RT may cause, in organs and tissues close to the planning target volume (PTV), but also in organs at higher distances, an increased risk for late and very late clinically relevant side effects that have a major impact on quality of life.

Technological developments in RT, such as intensity modulated radiotherapy (IMRT)/Volumetric modulated arc therapy (VMAT) and deep inspiration breath hold, have allowed for a significant reduction of cardiac doses. However, as there appears to be no threshold dose below which cardiac complications do not appear; radiation-induced cardiac diseases remain potential severe late complications of BC radiotherapy.

Therefore, there is an urgent need for primary and secondary preventive measures. Primary prevention includes radiation dose optimisation to the most critical structures of the heart. Secondary prevention requires identification of patients at risk as early as possible after RT treatment.

Long before the onset of clinically significant cardiac complications occurring many years after RT, subclinical cardiac changes can occur over weeks, months or first years after RT, that can be detected using anatomical and functional cardiac imaging or circulating biomarkers.

#### *Anatomical and functional cardiac imaging*

Using a recent advanced echocardiographic technique, automated 2D-speckle-tracking echocardiography / cardiac strain, for detecting and quantifying subtle disturbances in left ventricular systolic function; strain and strain rate were significantly decreased (mean 5%) during the first year following breast RT. In patients with left-sided BC global longitudinal strain and apical strain was diminished. The basal regions showed a compensatory increase in function, though not enough to compensate for the global functional loss resulting in a decrease in the global

longitudinal strain. Tuohinen et al. also showed deterioration in basal anterior strain segments after right-sided radiotherapy, whereas the global function remained unaffected. They also observed with tissue Doppler imaging that RT increased ECHO-ST density in the RV free wall and in the septum at the end of RT in patients with left-sided BC, but there were no changes observed in cardiac ECHO-ST density in patients with right-sided BC.

Cardiac computed tomography (CT) without contrast and coronary computed tomography angiography (CTCA) provides morphological information of the coronary arteries, visualization of the coronary artery anatomy, determination of plaques and stenosis of the coronary arteries, and determination of the calcium artery calcium (CAC) score. This reflects the evolution of coronary artery disease. Three studies have measured the amount of CAC in the years following RT treatment for BC. In two studies, no elevated CAC scores in BC patients were found 5 to 15.7 years after RT treatment, whereas 1 study did find an increase in CAC score depending on radiation dose to the heart. Of the studies that did not find a CAC score increase, one did not include baseline CAC scores and the other only included a relatively small number of patients, which makes it difficult to draw definitive conclusions from these two studies. In young Hodgkin's lymphoma survivors (all under 55 years) elevated CAC scores have been found in the 5 to 35 years after RT. Based on the analysis of 15 segments of coronary arteries per patient, an increase of calcified and non-calcified plaques of around 15% was observed during a 2-year follow-up. A study concerning the general population investigated CAC scores at baseline and after 10 years of follow-up. The results showed that the diagnosis of cancer and its treatments were significantly associated with the development of CAC, even after accounting for cardiac risk factors. The results of these studies suggest that RT is associated with increased CAC scores in the long term and therefore supports the hypothesis that accelerated atherosclerosis is one of the mechanisms contributing to an increase of radiotherapy induced cardiac events after cardiac irradiation.

Finally, with cardiac magnetic resonance imaging (MRI), which is considered the gold standard to characterize myocardial tissue and to measure ventricular volumes and function, it has been shown that right ventricular systolic function (TAPSE) was decreased in a BC cohort at 24 months. Furthermore, temporary ejection fraction decreases were observed on MRI (in patients treated with 3DCRT and not in patients treated with IMRT) at 6 months resolving at 24 months. Left (MAPSE) and right (TAPSE) ventricular systolic function determined by MRI were reduced at 24 months (but still within normal range) for the whole cohort. Furthermore, with T1 mapping, a promising technique to quantify morphologic tissue injuries, it was shown in cancer survivors (including BC patients) that interstitial/diffuse myocardial fibrosis was elevated 3 years after anthracycline-based chemotherapy independent of the underlying cancer or comorbidities, suggesting that imaging biomarkers of interstitial fibrosis are related to prior receipt of potentially cardiotoxic cancer treatment.

